#### 4.2.4. Sensitivity Analyses

Sensitivity analyses for the primary estimand will be conducted under the treatment policy framework using the Full Analysis Set. These sensitivity analyses will only be needed where the

JZP385 group demonstrates a statistically significant improvement over the placebo group, based on the criteria outlined in Section 2.1.

[figure not shown]
To test the robustness of the underlying MAR assumption of MMRM, reference-based imputation methods utilizing the joint modeling methods proposed originally by James H. Roger ([Rogers JH, 2012](#)) will be used. A tipping point analyses (delta adjusted method) will be further conducted to explore the influence of missingness on the conclusion from the main analytic approach by examining a wide range of possible assumptions.

#### 4.2.4.1. Control-based Imputations

The control-based imputation on the joint modeling method is proposed. For participants who early discontinued due to other reasons, missing data will be imputed assuming MAR. Control-based imputation (CBI) method assumes a mean and variance based on the control group for participants who withdrew from the JZP385 group at the time of withdrawal to the imputed timepoint, with the observed values prior to withdrawal still considered, thus a slow decay back toward the control group mean eventually. ([Carpenter JR, 2013](#)) This method assumes that from withdrawal onwards, participants in the active treatment group will progress back to the participants in the control group.

Figure 3 illustrates MAR estimates versus the estimates derived from CBI (assuming study participants withdraw at Visit 2 and a lower response indicates improvement).

**Figure 3: Control Based Imputation (MAR vs CBI)**

The control-based imputation will be implemented through steps below:

Treatment dropouts and missing observations at Weeks 5, 9, 13 and 17 will be imputed using the multiple imputation method. MI procedure in SAS will be used to impute the missing TETRAS composite outcome score at the missed visit to create 20 complete datasets.

The missing data pattern will be checked and reported. If any non-monotone missing data pattern is observed, 2 separate steps will be followed to complete the imputation, starting with Step 1. If a monotone missing data pattern is observed, skip to Step 2 directly (set imputation number to 20 instead).

Step 1: The Markov Chain Monte Carlo (MCMC) method will be used with a single chain to impute TETRAS composite outcome score by treatment, baseline stratification group as well as baseline TETRAS composite outcome score to create 20 imputed datasets with monotone missing patterns. Set the seed as 8715942. Imputed scores should be rounded to nearest integer, with the minimum and maximum possible score set to 0 and 42 respectively, which corresponds to the range of possible TETRAS composite outcome score.

Step 2: The predictive mean matching (PMM) method will be used to impute the remaining missing scores for the 20 imputed datasets with monotone missing patterns. The imputation procedure will use monotone statement to create 1 compete dataset for each of the monotone datasets from Step 1, with model variables to include treatment, baseline stratification group, as well as TETRAS composite outcome score at scheduled visits from Baseline to Weeks 5, 9, 13 and 17. Set the seed as 4985135 and number of closest observations to 2.

For participants who discontinued the study early due to either lack of efficacy or an adverse event, the post-discontinuation values imputed through Steps 1 and 2 will be set to missing and rederived using CBI method (MNAR).

The imputed datasets with a mixture of MAR and MNAR imputations will be analyzed separately using the MMRM model specified in 4.2.2, and then final inference will be pooled using the MIANALYZE procedure and reported.

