7.1.1. Participants Remaining in the Study After Study Intervention Discontinuation

Discontinuation from study intervention does not represent discontinuation from the study. For participants who discontinue study intervention early, every effort should be made to attend Efficacy Follow-up Visits through 17 weeks after the first dose of study intervention. After completing the E/D visit, if the participant is willing to attend Efficacy Follow-up Visits after the study intervention is discontinued, the guidelines for scheduling efficacy visits are as follows:

- For participants who discontinue study intervention prior to the Week 9 Visit, it is encouraged to schedule 3 additional Efficacy Follow-up Visits at 9, 13, and 17 weeks after first dose.
- For participants who discontinue study intervention after the Week 9 Visit but prior to the Week 13 visit, it is encouraged to schedule 2 additional Efficacy Follow-up Visits at 13 and 17 weeks after first dose.
- For participants who discontinue study intervention after the Week 13 Visit but prior to the Week 17 Visit, it is encouraged to schedule an additional Efficacy Follow-up Visit at 17 weeks after first dose.
- Participants should be scheduled for the Safety Follow-up Visit 2 weeks after the last dose of study intervention. However, 1 of the Efficacy Follow-up Visits can be combined with the participant's Safety Follow-up Visit if the Efficacy Follow-up Visit is scheduled to occur within 2 weeks after the participant's last dose of study intervention.

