7.2. Participant Discontinuation/Withdrawal from the Study

- A participant may withdraw from the study at any time at his/her own request or may be withdrawn at any time at the discretion of the investigator for safety, behavioral, or compliance reasons.
- At the time of discontinuing from the study, an E/D Visit should be conducted. In addition, a Safety Follow-up Visit should be conducted as shown in the SoA ([Section 1.3](#)). See the SoA for data to be collected at the time of study discontinuation and at the Safety Follow-up Visit and for any further evaluations that need to be completed. The participant will be permanently discontinued both from the study intervention and from the study at that time.
- If the participant withdraws consent for disclosure of future information, the sponsor may retain and continue to use any data collected before such a withdrawal of consent.
- If a participant withdraws from the study, he/she may request destruction of any samples taken and not tested, and the investigator must document this in the site study records.

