9.4.1.5. Dropouts and Missing Data

Every effort will be made to limit premature discontinuation of the study and ascertain completeness of the data collection. Efficacy Follow-up Visits at Weeks 9, 13, and 17 will be conducted as needed for participants who discontinue study intervention but remain in the study to complete scheduled efficacy assessments (see [Section 1.3](#)).

However, missing data caused by reasons defined outside the scope of intercurrent events can still occur (eg, intermittent missing data due to noncompliance). In that case, the MAR assumption will be considered appropriate and missing data will be handled accordingly by MMRM or MI.

[Figure 1](#) provides a flowchart depicting how missing data due to early discontinuation will be addressed for the main analyses of the primary and key secondary efficacy estimands.

Figure 1: Handling of Missing Data Due to Early Discontinuation for the Primary and Key Secondary Efficacy Endpoints

Abbreviations: AE = adverse event; LOE = lack of efficacy; MAR = missing at random; MI = multiple imputation; MMRM = mixed-effect model with repeated measures; MNAR = missing not at random; NRI = non-responder imputation.

Under the main analytical approach, missing data will be assumed to be MAR for participants who do not complete the Efficacy Follow-up Visit(s). The MMRM (for the TETRAS composite outcome score) and MI (for CGI-S response) assume participants with missing data would have efficacy outcomes similar to those participants in their respective study intervention group, randomization stratum, and initial trajectory who completed the study. The MMRM produces an estimate of the treatment effect via restricted maximum likelihood estimation, and a 2-step MI method produces a group of statistical estimates and will be pooled using Rubin's rule.

Under the sensitivity analyses, control-based imputations (for TETRAS composite outcome score) and NRI (for CGI-S response) will be used to treat missing data among participants discontinued due to an AE or lack of efficacy. Tipping-point analyses will be further conducted to assess the robustness of the underlying MAR assumption used in MMRM and MI.

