#### 4.1.3. Intercurrent Events Strategies

For the primary and key secondary estimands analysis, the following ICEs should be considered:

- Treatment discontinuation due to lack of efficacy or an AE; and any other reasons including study treatment noncompliance.
- Additional/alternative therapies used after the first dose of study intervention including PRN use of PD medications, switching PD treatments, or any dose/regimen change of background PD treatments.

The ICEs will be handled using 2 approaches:

[figure not shown]
- For the main analytical approach, the treatment policy strategy will be used to address all defined ICEs. The treatment policy strategy is defined as the effect of the randomized intervention over the study period regardless of the occurrence of an intercurrent event. Per the treatment policy, data should be collected after the occurrence of intercurrent event and will be included for statistical analyses and data interpretation.
- For the supplemental analysis approach, hypothetical strategy will be used to address post-ICE observations up to Week 17 due to discontinuation of study treatment. For ICEs of additional/alternative therapies used after the first dose of study treatment, treatment policy should still be applied. The hypothetical strategy is defined as the pharmacologic effect of JZP385 compared to placebo assuming the intercurrent event did not happen with continuation of randomized treatments for the duration of the study. Analysis will be conducted using data collected at time points that are obtained at or prior to participants discontinuing from study treatment and combined with modeled values for post-discontinuation timepoints where the underlying assumptions are considered as appropriate.

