**Figure 2: Management of Missing Data due to Early Discontinuation for the Primary and Key Secondary Efficacy Estimands**

Under the main analytical approach, missing data will be assumed to be MAR for participants who do not complete the Efficacy Follow-up visit(s). The MMRM (for the TETRAS composite outcome score) and MI (for CGI-S response) assume participants with missing data would have efficacy outcomes similar to those participants in their respective study intervention group, randomization stratum, and initial trajectory who completed the study. The MMRM produces an estimate of the treatment effect via restricted maximum likelihood estimation, and a 2-step MI method produces a group of statistical estimates and will be pooled using Rubin's rule.

Under the sensitivity analyses, control-based imputations (for TETRAS composite outcome score) and NRI (for CGI-S response) will be used to treat missing data among participants discontinued due to an adverse event or lack of efficacy. Tipping-point analyses will be further conducted to assess the robustness of the underlying MAR assumption used in MMRM and MI.

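### SAP 4.2.4.1 triggers control-based imputation by the reason for leaving the study, not for stopping treatment, so read literally some adverse-event stoppers can stay MAR in the analysis meant to challenge MAR

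*SAP*

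**What the plan says.** SAP 4.2.4.1 first imputes all missing TETRAS composite scores under MAR in two steps. It then singles out one group, "For participants who discontinued the study early due to either lack of efficacy or an adverse event". Their imputed values after discontinuation are blanked and re-derived by the control-based method. The same section gives the default: "For participants who early discontinued due to other reasons, missing data will be imputed assuming MAR".

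The general missing-data text uses a looser trigger. SAP 4.1.4 says the sensitivity methods "will be used to treat missing data among participants discontinued due to an adverse event or lack of efficacy". Protocol 9.4.1.5 says they "will be used to treat missing data among participants discontinued due to an AE or lack of efficacy". Neither says whether treatment or the study is what was discontinued.

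Elsewhere the two events are kept apart:

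- Protocol 7.1.1: "Discontinuation from study intervention does not represent discontinuation from the study". Later visits take place "if the participant is willing to attend Efficacy Follow-up Visits after the study intervention is discontinued".
- Protocol 7.2: "A participant may withdraw from the study at any time at his/her own request".
- SAP 4.1.3 defines the intercurrent event as "Treatment discontinuation due to lack of efficacy or an AE; and any other reasons including study treatment noncompliance".
- SAP 4.2.5 (the hypothetical-strategy analysis) is keyed to treatment discontinuation.
- SAP 4.7.1 summarises the primary reason for those who stopped study treatment early.

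**The concern.** Control-based imputation is one of the two planned checks on the MAR assumption behind the primary MMRM, and the only one that depends on the reason for stopping. It is aimed at active-arm participants whose benefit is least likely to persist: those who stop drug for an adverse event or lack of efficacy and then have no data. If the trigger is the study-exit reason, some of them can be missed, because the reason for leaving the study need not match the reason for stopping drug, and some never formally leave. The control-based estimate would then sit closer to the MAR estimate because of the selection rule, not because the result is robust.

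Under SAP 4.2.4 these analyses run only if the primary comparison is significant, which is when a weakened check matters. A programmer who finds the study named in 4.2.4.1 and treatment named in 4.2.5 could reasonably code two different events.

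A linked gap is that 4.2.4.1 does not say whether the post-discontinuation period starts at the last dose or at study exit. If at exit, visits missed between the two would also stay MAR.

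**Working it through.** **1. Who is covered under each reading.** Take an active-arm participant who stops drug for an adverse event.

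| What happens next | Trigger = study-exit reason (literal) | Trigger = treatment-stop reason |
|---|---|---|
| Leaves the study, adverse event recorded as the exit reason | Control-based | Control-based |
| Attends the E/D visit, declines follow-up, own request recorded as the exit reason | MAR (other reason) | Control-based |
| Stays in the study, misses Week 17 | MAR (study not discontinued) | Control-based |
| Attends the Week 17 Efficacy Follow-up | Observed value used | Observed value used |

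The readings differ in rows 2 and 3. Row 2 depends on how the site records the exit reason, for which the documents give no rule.

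**2. The plan's own figures (SAP 5).** Difference 3.0, SD 6.0, 2-sided 0.05, two-sample t-test: n = 63.77, so 64 per arm, with power 80.1%. With 20% dropout, 64 / 0.80 = 80 per arm, 160 in total. This reproduces the plan and leaves 80 − 64 = 16 planned dropouts per arm. The documents do not split these by reason.

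**3. Illustrative size per affected participant.** The SAP describes a method that keeps the pre-withdrawal values and lets the mean drift back to control. I take this as copy-reference. For a participant last seen at visit k of Weeks 5, 9, 13, the Week 17 conditional means under MAR and copy-reference differ by

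D = d17 − b × (sum of treatment effects at the observed visits), with b = ρ / (1 + (k − 1)ρ),

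where d17 = 3.0 is the planned Week 17 effect. Assumptions not in the documents are exchangeable correlation ρ = 0.6 and the effect profile. Two profiles are shown: flat at 3.0, and rising 1.5, 2.5, 3.0, 3.0 at Weeks 5, 9, 13, 17.

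| Last visit | b | Flat effect | Rising effect |
|---|---|---|---|
| Week 5 | 0.600 | 3.0 − 0.600 × 3.0 = 1.20 | 3.0 − 0.600 × 1.5 = 2.10 |
| Week 9 | 0.6/1.6 = 0.375 | 3.0 − 0.375 × 6.0 = 0.75 | 3.0 − 0.375 × 4.0 = 1.50 |
| Week 13 | 0.6/2.2 = 0.273 | 3.0 − 0.273 × 9.0 = 0.55 | 3.0 − 0.273 × 7.0 = 1.09 |
| Mean (equal weights) | | 0.83 | 1.56 |

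**4. Illustrative shift in the sensitivity estimate.** Shift = (n / 80) × mean D, where n is the number of active-arm participants left MAR who should have been control-based.

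| n | Flat | Rising | Bound: all 3.0 points lost at once |
|---|---|---|---|
| 4 | 0.04 | 0.08 | 0.15 |
| 8 | 0.08 | 0.16 | 0.30 |
| 12 | 0.12 | 0.23 | 0.45 |

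The bound overstates the shift, because the SAP describes a gradual return to control. At the extreme, if every such participant has another exit reason, the control-based estimate equals the MAR estimate and tests nothing.

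**5. Scale.** The planning standard error is 6.0 × √(2/64) = 1.06 points, so 0.23 is about a fifth of it. Having n = 12 would need 12/16 = 75% of the planned active-arm dropouts to be affected.

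**The case against.** The best defence is that the SAP uses the study loosely. SAP 1.2.1 sends those who discontinue the study early into Safety Follow-up, whereas note b of the protocol's Schedule of Activities requires that visit of anyone who stops study intervention, whether or not they stay in the study. The same phrase there stands in for stopping treatment. SAP 4.1.4 is headed by treatment dropouts, the implementing steps in 4.2.4.1 open with the same term, and the reasons belong to treatment discontinuation in 4.1.3 and 4.7.1. The flowcharts in SAP 4.1.4 and Protocol 9.4.1.5 may settle the matter but are not shown in the copy reviewed. This stands as evidence of likely intent. It does not change the words of the operative step, and no visible text says that the treatment-stop reason governs there.

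Two further points stand. A site may record the adverse event as the exit reason, in which case control-based imputation applies even on the literal text. And SAP 4.2.4.2 worsens imputed active-arm values with no reason filter. It does not, however, supply the reason-specific control-based estimate that both documents promise.

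A reader might infer that the SAP definitely exempts these participants, that they escape every challenge to MAR, or that the primary result is biased. The documents support none of these. A reader might also fear that observed follow-up data would be overwritten, but 4.2.4.1 resets only values produced by the two imputation steps.

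**Conclusion.** The point holds as a wording gap with a real consequence if followed literally: the trigger names the wrong event, and participants the analysis is meant for can stay MAR. It does not show that the sponsor intends this.

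The primary estimate, its p-value and the Type I error rate do not change. Under the assumptions above, the sensitivity estimate would be too favourable by about 0.04 to 0.12 points (flat effect) or 0.08 to 0.23 points (rising effect) when 4 to 12 of 80 active participants are affected. The correlation, the effect profile and the counts are assumptions, not figures from the documents. The larger range depends on the rising profile and should not be quoted without it. The size is modest; the case for change rests on the trigger.

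**What to change.** In SAP 4.2.4.1:

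- Apply the control-based step to participants who discontinued study treatment early because of lack of efficacy or an adverse event, whatever the reason for leaving the study.
- Apply control-based values to the missing visits after the treatment stop date.
- Reword the MAR default for other reasons so that it refers to the same event.

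In SAP 4.1.4, use the same trigger wording, and check that the flowchart agrees.

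The cost is a few words. The reason for stopping study treatment is already summarised under SAP 4.7.1, so no new data are needed.

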#### 4.2.4.2. Tipping Point Analyses

To further assess the robustness of the main analytic approach, the tipping point analyses include a wide range of analysis assumptions by applying an adjustable delta parameter on the continuous efficacy outcome in a gradual manner, as the value of this parameter changes, the observed statistical significance could be overturned ([O'Kelly M, 2014](#)). The tipping point analyses could possibly extend beyond reference-based imputation methods described above by including scenarios where participants who withdraw the study early tend to perform even worse than participants from the control group.

The marginal delta approach will be used for tipping point analyses by following Steps 1 and 2 specified above (4.2.4.1) followed by Step 3:

Step 3: For participants in a JZP385 treatment group, make the imputed value worse by an increment of delta, with the initial delta value set at 0, which is equivalent to the MAR estimate, and increases delta value by 10% of the maximum observed treatment difference among all dose groups at each time, until the tipping point is detected.

The primary analysis will be reperformed, using the MMRM model specified in 4.2.2, for each imputed dataset, at each delta. The results from the datasets, at each delta, will be pooled, using the MIANALYZE procedure.

The delta identified at which the results are no longer statistically significant will be the tipping point. After the tipping point is determined, clinical judgement will be applied to the plausibility of the assumptions underlying this tipping point.

#### **4.2.5. Supplemental Analysis**

For supplemental analysis, ICE defined relating to treatment discontinuation will be treated as if participants did not experience them by assuming the pharmacologic effect of JZP385 continued throughout the duration of study (hypothetical strategy). The Full Analysis Set will be used for supplemental analysis and the analysis will be repeated over mITT.

A similar MMRM model specified for the main analytical approach will be used, observations after treatment discontinuation will be set to missing (with no LOCF imputation) and analyzed under MMRM assuming MAR.

## 4.3. Key Secondary Estimands

### 4.3.1. Definition of Key Secondary Estimands

The attributes of the key secondary estimand are listed in Section 1.1.

The CGI-S is a 5-point Likert-type ordinal scale. The responses to this investigator-completed scale range from 1 to 5 and correspond to the following categories:

- No limitations (1)
- Mild (2)
- Moderate (3)
- Marked (4)
- Severe (5)

For analysis purposes, CGI-S will be treated as categorical variable where a response is defined as a  $\geq 1$ -point decrease (improvement) from Baseline to Weeks 5, 9, 13 and 17. For the estimator, the proportion of participants who have achieved the response at Week 17 will be compared between JZP385 and placebo groups. As the study requires all participants to have a baseline CGI-S rating of  $> 2$  (i.e., at least moderate) to be randomized, it is not anticipated that a situation will occur where a participant cannot show an improvement due to having a baseline score of 1 (no limitations).

### 4.3.2. Main Analytical Approach

The analysis will be conducted under the treatment policy framework using the Full Analysis Set.

The main estimator of the key secondary estimands will be analyzed using the CMH test adjusting for the stratification factor at randomization (Baseline TETRAS composite score  $\leq 17$  or  $> 17$ ). Number of responders in each group, proportion as well as 95% CI (Wilson score method) will be reported and presented in a histogram at Weeks 9, 13 and 17. The 2-sided p-values from the CMH test, the unadjusted treatment difference as well as the adjusted treatment difference in proportion using the weighted average of the treatment differences across strata with CMH weights, and the associated 2-sided 95% CI using a normal approximation to the weighted average will be derived and reported at Weeks 9, 13 and 17.

Treatment dropouts and missing observations for the main analytic approach will be handled through MI. Missing values at Week 17 for CGI-S will be imputed using the multiple imputation method, a method relies on observed values from similar participants who remained in the study to bridge information to deduce missing observations. MI procedure in SAS will be used to impute missing CGI-S score at the scheduled visit to create 20 complete datasets.

The missing data pattern will be checked and reported at Baseline, Weeks 5, 9, 13 and 17. If any non-monotone missing pattern is observed, two separate steps will be followed to complete the imputation.

Step:1 the Markov Chain Monte Carlo (MCMC) method will be used with a single chain to impute missing CGI-S scores by treatment, baseline stratification group as well as baseline CGI-

S score to create 20 imputed datasets with monotone missing patterns. Set the seed as 8715942. Imputed scores should be rounded to nearest integer, set minimum and maximum possible score to 1 and 5 respectively, which corresponds to the range of CGI-S.

Step: 2 the predictive mean matching (PMM) method will be used to impute the remaining missing CGI-S scores for the 20 imputed datasets with monotone missing patterns. The imputation procedure will use monotone statement to create 1 compete dataset for each of the monotone datasets from Step 1, with model variables include treatment, baseline stratification group, as well as CGI-S score at scheduled visits from Baseline to Weeks 5, 9, 13 and 17. Set the seed as 4985135 and number of closest observations to 2.

The imputed datasets will be analyzed using CMH test, and the final inference will be pooled using SAS procedure MIANALYZE.

An example SAS code for CMH analysis is as follows:

```

PROC SORT DATA = CGIS;
BY IMPUTESEQ VISIT TRT STRATUM DECENDING RESPONSE;
RUN;

PROC SQL;
CREATE TABLE ADDIN AS
SELECT DISTINCT IMPUTESEQ, VISIT, TRT, STRATUM, 1 AS RESPONSE
FROM CGIS;
QUIT;

DATA CMH;
MERGE CGIS (IN=A) ADDIN (IN=B);
BY IMPUTESEQ VISIT TRT STRATUM DECENDING RESPONSE;
IF B AND NOT A THEN WGT = 0;
ELSE WGT = 1;
RUN;

*Adjusted (Stratified) Difference and CMH TEST;
PROC FREQ DATA=CMH;
BY IMPUTESEQ AVISITN;
TABLES STRATUM*TRT*RESPONSE/RISKDIFF (COMMON CL=(NEWCOMBE)) CMH;
WEIGHT WGT/ZEROS;
RUN;

*Unadjusted (Unstratified) Difference;
PROC FREQ DATA=CMH;
BY IMPUTESEQ AVISITN;
TABLES TRT*RESPONSE/RISKDIFF CMH;
WEIGHT WGT/ZEROS;
RUN;

```

